# 5.3 Overview of Preclinical Study Results

# 1) Overview of nonclinical efficacy and safety studies

Study items	Results
Transplantation of human iPS	The corneal epithelium was reconstructed, and corneal
cell-derived corneal epithelial cell	transparency and barrier function were observed
sheets into rabbit disease models	(follow-up period: 2 weeks, $n = 7$ ).
	No abnormalities such as tumor formation or cell
	migration were observed (follow-up period: 3 weeks, n =
	7).
	Sample tested: Processed product for use in nonclinical
	studies (iPS cell line: 1383D2)

# 2) Overview of nonclinical tumorigenicity studies

Study items	Results
Study on subcutaneous	Autopsy was performed after a 16-week follow-up period.
transplantation (cell sheet	Tumor formation was not observed.
administration) in	(n=1)
immunocompromised mice (1)	
Study on subcutaneous	Autopsy and histopathological observations were
transplantation (cell sheet	performed after a 16-week follow-up period. Tumor
administration) in	formation was not observed.
immunocompromised mice (2)	(n=12)
Karyotyping	No cytogenetic abnormalities were observed.
	(n=1)
Cell proliferation characteristic	Cell transformation and immortalization were not
analysis (serial passaging)	observed.
	(n=1)
Study to rule out the presence of	Below detection limit to 2.5 (copies/RNA 50 ng)
undifferentiated iPS cells (1)	(n=6)
(measurement of LIN28A	All conformed to the reference value of $\leq 20$
expression)	
Study to rule out the presence of	No undifferentiated iPS cell colonies were detected.
undifferentiated iPS cells (2)	(n=1)
(reculture in medium used for iPS	
cells)	
Genome analysis	No genomic abnormalities were observed.
	(n=1)

# 3) (Reference data) Overview of nonclinical tumorigenicity studies using the processed cell product for use in nonclinical studies

Study items	Results
Study of subcutaneous transplantation in immunocompromised mice (cell suspension administration)	Tumor formation was not observed (follow-up period: 16 weeks; nude mice: n = 10, NOD-SCID mice: n = 21).
Study of subcutaneous transplantation in immunocompromised mice (cell sheet administration)	Tumor formation was not observed (follow-up period: 16 weeks; NOD-SCID mice: n = 6, NOG mice: n = 2).

Karyotyping	No cytogenetic abnormalities were observed (n = 5).
Cell proliferation characteristic analysis (serial passaging)	Cell transformation and immortalization were not observed (n = 3).
Study to rule out the presence of undifferentiated iPS cells (1) (measurement of LIN28A expression)	LIN28A expression was very low (2.4 copies to $\leq$ detection limit, $n = 24$ ).
Study to rule out the presence of undifferentiated iPS cells (2) (reculture in medium used for iPS cells)	No residual undifferentiated iPS cell colonies were detected ( $n = 22$ ).
Genome analysis	Although SNV/InDel analysis showed mutation sites corresponding to the PMDA/Census list and CNV analysis showed loss, no homozygous mutations directly affecting gene expression were detected in either analysis (samples derived from cell line 1383D2, n = 2).

#### 6. Treatment Plan and Criteria for Treatment Modification

# 6.1 Transplantation of Allogeneic iPS Cell-derived Corneal Epithelial Cell Sheet

The protocol treatment for this research is defined as allogeneic iPS cell-derived corneal epithelial cell sheet (iCEPS) transplantation.

It will be performed in accordance with the following procedures.

- 1) Upon receipt of the iCEPS from the person in charge of production, the principal investigator or subinvestigator confirms whether the iCEPS was produced in accordance with the Specific Processed Cell Product Summary using the release decision chart and decides whether or not to administer the product. They also check the condition of the product preservation solution (to ensure no turbidity or foreign matter). The product must not be used if any turbidity or foreign matter is observed.\*
- 2) The product is transplanted under local anesthesia or systemic anesthesia. Transplantation of iCEPS is carried out by hospitalization, and the scheduled hospitalization period is about 3 to 4 weeks.
- 3) The conjunctiva scar is removed as much as possible from the cornea of the injured eye.
- 4) Symblepharon, if any, is treated simultaneously by conjunctival sac plasty or amniotic membrane transplantation to the sclera as necessary.
- 5) The temperature-responsive culture dish containing the cell sheet is removed to a clean area using sterile forceps or another suitable instrument.
- 6) The cell sheet support is grasped and lifted with sterile forceps or another suitable instrument, and the cell sheet is carefully peeled off. The cell sheet on the temperature-responsive culture dish is transplanted without reversing the top and bottom.

- 7) iCEPS is placed on the transplantation site. The cell sheet is cut along the perimeter with a scalpel, scissors, or trepan to remove, and the cell sheet is left as it is for approximately 15 minutes. Attachment of iCEPS to the transplantation site is confirmed.
- 8) After transplantation, a soft therapeutic contact lens is placed, tarsorrhaphy is performed as necessary, the eyelid is closed and fixed, and the subject is placed at rest.
  - \* The results of genetic analysis performed for reference purposes will be available approximately 4 months after transplantation. If a genetic abnormality is found, the subject will be informed, more careful post-treatment follow-up will be conducted, and appropriate measures will be taken.

# 6.2 Administration of Medications After iCEPS Transplantation

- 1) All subjects will receive systemic and local corticosteroids and local antibiotics. The medications, dose, and duration of administration may be modified as appropriate based on the subject's condition.
- 2) An immunosuppressive agent (cyclosporine) will be administered after iCEPS transplantation to the following subjects:
  - (1) iCEPS transplantation cases 1 and 2
  - (2) iCEPS transplantation cases 3 and 4, if uncontrolled rejection occurred in 1 or both of the first 2 cases, in accordance with "9.4 Midterm Evaluation"

In general, cyclosporine should be administered from the day of iCEPS transplantation (after transplantation) until Week 52 after transplantation. Trough levels should be checked, and the dose should be adjusted accordingly.

3) Immunosuppressive agents other than cyclosporine (e.g., mycophenolate mofetil) may generally be used during the perioperative period to treat the primary disease.

Compliance with medication and eye drop use will be confirmed by collecting empty medication sheets and bottles from subjects and interviewing the subjects.

# 6.3 Prohibited Concomitant Drugs and Therapies

#### 6.3.1 Prohibited concomitant drugs

None

#### 6.3.2 Prohibited concomitant therapies

None

Drugs and therapies used concomitantly during the clinical research period will be documented in the Case Report Form (CRF).

#### 6.4 Discontinuation of Subjects

#### 6.4.1 Discontinuation criteria

In the event of any of the following items, the principal investigator or subinvestigator should discontinue the clinical research of the relevant subject.

- 1) When the subject withdraws consent
- 2) When the subject experiences an unacceptable adverse event
- 3) When iCEPS shows poor performance or the condition of the subject worsens, and the clinical research should be discontinued in the opinion of the investigator or subinvestigator
- 4) When ineligibility of the subject is revealed after the start of the clinical research
- 5) When the subject is lost to follow-up because he/she does not visit the research site
- 6) If the subject becomes pregnant before iCEPS is transplanted
- 7) Other cases where the investigator or subinvestigator considers it necessary to discontinue the clinical research

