#### 6.4.2 Procedures and follow-up for subjects who discontinue the research

Appropriate action should be taken for the subject according to the reason for discontinuation, and mandatory examination/survey at the end of the research should be completed within 7 days after discontinuation as far as practicable to evaluate the condition of the subject at the time of discontinuation. The results should be documented in the CRF.

Follow-up of the subject is continued after discontinuation of the clinical research as far as practicable, regardless of the reason for discontinuation, and the results are entered in the CRF. If a subject discontinued the research due to an adverse event, he/she should be followed up until his/her condition/laboratory values improve or stabilize as far as practicable. If a subject does not come to the research site in the course of the research, the reason and clinical course should be followed up using an appropriate method (e.g., phone calling), and the results should be documented in the medical record and CRF.

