# 9. Definition of Efficacy and Safety Evaluations and Endpoints

# 9.1 Primary Endpoint

Safety will be evaluated by collecting adverse event data.

Evaluation period: From the day of iCEPS transplantation (during transplantation) to Week 52 after iCEPS transplantation or the date of discontinuation

Recording method: The subinvestigator acting as the subject's physician will record the details of each adverse event in the CRF (see "10.4 Response and Follow-up Investigation After Occurrence of Adverse Events"). The subinvestigator and physician-evaluator will make determinations regarding rejection and uncontrollable rejection.

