#### 1) LSCD stage

The LSCD stage will be determined by slit-lamp microscopy using the severity classification for LSCD (Fig. 1).

Target of evaluation: Target eye for iCEPS transplantation

Timing: At screening, day of iCEPS transplantation (before transplantation), and Weeks 2, 4, 8, 16, 24, 32, 40, and 52 after iCEPS transplantation or the discontinuation date

Method for recording determination: The consensus of the subinvestigator and physician-evaluator who made the determination will be recorded on a worksheet.

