#### (3) Major protocol violation

#### 13.2 Analyses and Methods

All statistical analyses will be performed after data lock for all subjects.

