# 13.4 Procedures for Handling Missing, Rejected, and Abnormal Data

Missing data will not be imputed. Handling of deviations or abnormal data will be determined at a Clinical Case Conference prior to data lock.

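### Safety and efficacy windows close at discontinuation, which can itself be driven by outcome, so events and visits after a graft failure fall outside the defined evaluation although the follow-up is recorded

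*Combined protocol and SAP*

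**What the plan says.** Discontinuation. Protocol 6.4.1 lists seven grounds. Two depend on how the patient is doing: criterion 2, an unacceptable adverse event, and criterion 3, "When iCEPS shows poor performance or the condition of the subject worsens". Criterion 3 applies only if the investigator or subinvestigator also judges that the patient's participation should end.

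Windows. Section 9.1 sets the evaluation period for the primary safety endpoint: "From the day of iCEPS transplantation (during transplantation) to Week 52 after iCEPS transplantation or the date of discontinuation". Section 8.10 says the same for adverse events. In 9.2 the LSCD stage is assessed at "Weeks 2, 4, 8, 16, 24, 32, 40, and 52 after iCEPS transplantation or the discontinuation date". The other graded items and visual acuity have the same timing; QOL is taken at Week 52 or at discontinuation.

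After discontinuation. Section 6.4.2 asks for the end-of-research examination within 7 days where feasible, and then says: "Follow-up of the subject is continued after discontinuation of the clinical research as far as practicable, regardless of the reason for discontinuation". The results go into the CRF.

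Analysis. Discontinuation excludes a patient from neither analysis set in 13.1. Section 13.2.1 tabulates discontinuations and post-enrolment deviations with reasons. The efficacy set, but not the safety set, has a third exclusion, "Major protocol violation", which is not defined. Section 13.4 rules out imputation and adds: "Handling of deviations or abnormal data will be determined at a Clinical Case Conference prior to data lock".

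**The concern.** Section 6.1 defines the protocol treatment as the transplantation itself. Once the sheet is on the eye, discontinuing a patient ends the evaluation but does not undo the exposure. Under criteria 2 and 3 the evaluation can end because of what has been observed, so the patients cut short are not a random subset.

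Two things are at stake. In safety, a new adverse event after a failing graft has led to discontinuation lies outside the primary endpoint. Yet section 7 relies on a 52-week period as sufficient to confirm safety in this first-in-human study. In efficacy, the later columns of the 13.2.4 tables and the right-hand end of the graphs would describe only the patients who continued.

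A secondary issue is the efficacy exclusion. It is undefined, the study is open-label, and subinvestigators help determine the endpoints at each evaluation time point (9.3). Nothing in the plan prevents an exclusion from being decided when outcomes are already visible.

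**Working it through.** **Step 1: inputs.** Planned sample size is 4 (section 7). Its rationale is feasibility: 100 patients a year × 10% eligible × 20% enrolling = 2 a year. That reproduces the stated rate, and 4 corresponds to two years of recruitment, a duration the section does not state. The primary window is 52 weeks (9.1). The graded efficacy items and visual acuity have 8 scheduled post-transplant visits: Weeks 2, 4, 8, 16, 24, 32, 40 and 52 (9.2).

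**Step 2: what happens to a discontinued patient.**

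- Membership of the analysis sets: kept in both (13.1).
- Status at the stop: examined (6.4.2), an efficacy assessment point (9.2), and reported with a reason (13.2.1).
- New adverse events after the stop: outside 8.10 and 9.1.
- Efficacy visits after the stop: outside 9.2, and not imputed (13.4).
- Follow-up under 6.4.2: recorded, but neither 13.2.3 nor 13.2.4 says how it is used.

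**Step 3: size, assuming one of four patients is discontinued at week w and the other three complete.** Planned safety time is 4 × 52 = 208 patient-weeks. Time lost from the window is 52 − w, and its share is (52 − w)/208.

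| Stop at week | Weeks lost | Share of 208 | Scheduled efficacy visits lost, of 8 |
|---|---|---|---|
| 2 | 50 | 24.0% | 7 |
| 8 | 44 | 21.2% | 5 |
| 24 | 28 | 13.5% | 3 |
| 40 | 12 | 5.8% | 1 |

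For the Week 8 case, the five missing visits are Weeks 16, 24, 32, 40 and 52.

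**Step 4: size of the efficacy exclusion.** One patient set aside as a violator removes 1/4 = 25% of the efficacy set.

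**Step 5: is there any sign that a patient was removed?** Supplementary Methods section 18 reports F values with (1, 3) degrees of freedom for pre- against post-operative contrasts. For such a contrast the second figure is n − 1, so n = 4. In the legible row of the ANOVA tables, F = 27.99, 15.21, 16.36 and 17.64 give P = 0.013, 0.030, 0.027 and 0.025 at (1, 3). These agree with the printed 0.01, 0.03, 0.03 and 0.02. With three patients, at (1, 2), they would be 0.034, 0.060, 0.056 and 0.052. The titles of Tables S8 and S9 also refer to four patients. Nothing suggests a removal.

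**The case against.** The best reply is that a failure cannot disappear under this plan. The patient remains in both sets, is examined at discontinuation, contributes that assessment, and is tabulated with the reason. Among four patients, any reader would see it. Section 13.2.3 lists whatever adverse events were collected without repeating the window. Section 10.1.1 ties the definition of an adverse event to the research period, which section 7 gives as calendar dates and not per patient. Section 10.4 follows events to resolution. Epithelial defect, conjunctivalisation and rejection are themselves expected adverse events (10.7), so the failure would normally be recorded as one. The violation exclusion does not touch the safety set, and a poor graft is not a violation.

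Most of this stands, and it disposes of several inferences a reader might draw:

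- That failures leave the results. They do not; what is cut is the period after them.
- That poor performance alone ends participation. Criterion 3 also needs the investigator's judgement.
- That 6.4.2 data are collected and then discarded. The plan does not say so; it is silent on their use.
- That success would read 3 of 3 instead of 3 of 4. The plan defines no success proportion; 13.2.4 plans tables and graphs over time, and 13.3 rules out estimation and testing.

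The reply does not remove the explicit end date in 8.10 and 9.1. Section 10.4 says how long to follow an event once it has arisen; it does not reopen the primary window for new ones. Where 10.1.1 and 13.2.3 can be read more widely than 9.1, the plan should say which governs.

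**Conclusion.** The point holds as one of truncation. The plan ends the primary safety evaluation and the efficacy assessments at a date that can be set by the outcome, and it gives no rule for using the follow-up it goes on to collect. In the Week 8 example this takes 44 of 52 weeks from one patient, or 21% of planned safety time, and five of eight efficacy visits. Across the stopping weeks tried, the loss of safety time runs from 5.8% to 24.0%. These figures assume one discontinuation among four and that 9.1 is applied as written; the documents forecast no discontinuation rate.

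The undefined efficacy exclusion is a secondary weakness. That it could be applied with outcomes visible is an inference from the open-label design. Section 13.4 places the handling of deviations before data lock but does not say that outcomes are reviewed first.

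A reader might conclude that the reported results are biased by removals. The documents do not support that: the degrees of freedom and table titles point to all four patients. The clinical criteria for discontinuing a patient are not in question here.

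**What to change.** 1. In 8.10, 9.1 and 9.2, evaluate every transplanted patient to Week 52 whatever the discontinuation status, ending only at withdrawal of consent or loss to follow-up.
2. In 13.2.3 and 13.2.4, state that follow-up recorded under 6.4.2 enters the listings, tables and graphs.
3. Where a later value is missing, mark the patient at that visit as discontinued, with the reason (for example poor performance), and do not leave a blank. Enter no grade: the scales have no failure category, and this keeps to the no-imputation rule in 13.4.
4. In the efficacy listings, show every transplanted patient who has post-transplant efficacy data, and flag major violators instead of dropping them.

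The cost is wording, through the revision route in 13.5, since 6.4.2 already provides for the data. That follow-up depends on feasibility and has no visit schedule of its own, so some values will be missing or off schedule. The efficacy picture may look slightly less favourable. Because 2.4 plans further trials on the basis of this one, the windows should also be corrected in any successor protocol.

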#### 6.4.2 Procedures and follow-up for subjects who discontinue the research

Appropriate action should be taken for the subject according to the reason for discontinuation, and mandatory examination/survey at the end of the research should be completed within 7 days after discontinuation as far as practicable to evaluate the condition of the subject at the time of discontinuation. The results should be documented in the CRF.

Follow-up of the subject is continued after discontinuation of the clinical research as far as practicable, regardless of the reason for discontinuation, and the results are entered in the CRF. If a subject discontinued the research due to an adverse event, he/she should be followed up until his/her condition/laboratory values improve or stabilize as far as practicable. If a subject does not come to the research site in the course of the research, the reason and clinical course should be followed up using an appropriate method (e.g., phone calling), and the results should be documented in the medical record and CRF.

# 6.5 Pregnancy During the Clinical Research Period

Investigators will instruct female subjects of childbearing potential and male subjects with a partner of childbearing potential to use two or more of the contraceptive methods listed in (1) to (4) or either of the contraceptive methods listed in (5) and (6), from the date of informed consent until the end of follow-up or discontinuation date. Subjects meeting these criteria should use appropriate contraception in accordance with their physician's instructions.

- 1) Use condoms
- 2) Use a pessary
- 3) Take oral contraceptives
- 4) Use a properly placed intrauterine device or intrauterine system

- 5) Male sterilization (bilateral vasectomy)
- 6) Female sterilization (bilateral tubal ligation)

When obtaining consent, the risks of pregnancy should be carefully explained in the informed consent form, the subject should be made clearly aware of the need to avoid pregnancy by using two or more of the methods listed in (1) to (4) or either of the methods listed in (5) and (6), and the subject's consent should be obtained with their full understanding of this information.

If a female subject becomes pregnant after informed consent but before iCEPS transplantation, the clinical research will be discontinued for that subject.

Investigators should instruct subjects to contact them in the event that a female subject or male subject's partner becomes pregnant after iCEPS transplantation. In case of such an occurrence, the investigator will promptly report the pregnancy to the principal investigator.

The investigator will discuss the risks associated with pregnancy continuation and the possible effects on the fetus with that subject or subject's partner and will provide advice. Appropriate medical care will be provided to that subject or subject's partner, and follow-up will continue until the end of the gestation period.

# 7. Planned Sample Size and Research Period

Planned sample size: 4 subjects

Research period: May 23, 2019 to March 31, 2024

Follow-up period: 1 year (52 weeks) after iCEPS transplantation

Additional safety monitoring period: 1 year (52 weeks) after the end of the follow-up period

\*After follow-up is complete, subjects will be encouraged to make regular outpatient visits and participate in follow-up throughout their lives as much as possible so that data can be collected and appropriate measures are taken as needed. Data collected through follow-up surveys will not be included in the analysis of results for this clinical research.

#### [Rationale for setting]

Osaka University Hospital, the site for this research, sees approximately 100 patients with LSCD each year.

Of these, only about 10% (10 patients) would likely be eligible for the protocol treatment. If we estimate that 20% of these eligible candidates would enroll, we would expect to be able to recruit 2 subjects per year. Therefore, the target sample size was set as 4 subjects.

The additional safety monitoring period of one year (52 weeks) was set in consideration of the following.

1) Overseas research of autologous cultivated corneal epithelial cell sheet transplantation

showed that if the reconstructed corneal epithelium is stable for one year after transplantation, stability of the corneal epithelium can be maintained thereafter, confirming a sustained therapeutic effect).

- 2) A report of long-term outcomes of autologous cultivated oral mucosal epithelial cell sheet transplantation showed that conjunctivalization, corneal opacity, and corneal neovascularization rates stabilize from one year after transplantation, with few changes.
- 3) As an follow-up period of about 6 months is generally required after ophthalmic surgery, 52 weeks can be considered a sufficient period to confirm safety.
- 4) A nonclinical tumorigenicity study of iCEPS, the specific processed cell product used in this research, showed no tumorigenesis in mice for 4 months after transplantation (see "5.3 Overview of Preclinical Study Results"). For the first-in-human transplantation of iCEPS, we believe that a safety confirmation period of 1 year (52 weeks) is reasonable, considering 1) to 3) above. A additional safety monitoring period of one year will be set, but follow-up will continue as long as possible thereafter to confirm the long-term safety of iCEPS.

